5.2. Inclusion criteria for enrolment

Deviations from inclusion criteria are not allowed because they can potentially jeopardise the scientific integrity of the study, regulatory acceptability or subject safety. Therefore, adherence to the criteria as specified in the protocol is essential.

All subjects must satisfy ALL the following criteria at study entry:

- Subjects who, in the opinion of the investigator, can and will comply with the requirements of the protocol (*e.g.* electronic Diary Card completion, number of blood draws, sputum sampling, pre- and post-bronchodilator spirometry, return for follow-up visits).
- A male or female between, and including, 40 and 80 years of age at the time of the first vaccination.
- Written informed consent obtained from the subject.

- Confirmed diagnosis of COPD (based on post-bronchodilator spirometry) with forced expiratory volume in 1 second (FEV₁) over forced vital capacity (FVC) ratio (FEV₁/FVC) < 0.7, **AND** FEV₁ < 80% and ≥ 30% predicted (GOLD 2 and 3).

- Current or former smoker with a cigarette smoking history of ≥ 10 pack-years.
Refer to the [glossary of terms](#) for the definitions of pack-years and of current and former smoker.

- Stable COPD patient* with documented history (e.g. medical record verification) of at least 1 moderate or severe AECOPD within the 12 months before Screening.

* Patient for whom the last episode of AECOPD is resolved for at least 30 days at the time of Screening.

Refer to the Study Procedures Manual (SPM) for details on what is accepted as documented history of AECOPD. Refer to [Table 2](#) for the definitions of moderate and severe AECOPD.

- Regular sputum producer.
- Capable to comply with the daily electronic Diary Card completion throughout the study period, according to investigator's judgement at Visit 1.

Refer to the SPM for recommendations on what is considered adequate compliance by Visit 1.

- Female subjects of non-childbearing potential may be enrolled in the study.
 - Non-childbearing potential is defined as current tubal ligation, hysterectomy, ovariectomy or post-menopause.
Refer to the [glossary of terms](#) for the definition of menopause.
- Female subjects of childbearing potential may be enrolled in the study, if the subject:
 - has practiced adequate contraception for 30 days prior to vaccination, and
 - has a negative pregnancy test on the day of vaccination, and

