6.5.2. List of study procedures during AECOPD-driven study visits and phone contacts

In addition to the scheduled study visits, *ad-hoc* AECOPD-driven study contacts will take place for each AECOPD occurring from first vaccination up to study conclusion. The procedures to be performed during these contacts are listed in [Table 8](#).

In case of AECOPD occurring before Visit 1, subjects should be treated outside the study according to standard practice. These subjects can only continue in the study if the entire Screening Visit is repeated after they are stable for at least 30 days.

Table 8 List of study procedures during AECOPD-driven study visits and phone contacts

Type of contact	AECOPD visit	End of AECOPD contact(s) (phone call[s] and/ or visit[s])
Timepoint	within 96 hours of onset symptoms	at least every 2 weeks as of AECOPD visit until AECOPD has resolved ^(a)
Sampling timepoint	AECOPD	
Record date of visit	●	
Physical examination	○	○ ^(b)
Chest X-ray ^(c)	●	
Confirm AECOPD and record its start date	●	
Blood sampling:		
For biomarkers (~12.8 mL)	●	
For haematology assessment (~2 mL)	●	
Sputum sampling ^(d)	●	
HRQOL questionnaires:		
CAT	x	
mMRC	x	
Record healthcare use for AECOPD (medical record review)	○	●
Record AEs	●	●
Report SAEs	●	●
Report pregnancies ^(e)	●	●
Record concomitant medications/products and vaccinations	●	● ^(b)
Record intercurrent medical conditions requiring medical attention	●	●
Record AECOPD severity	○	●
Record AECOPD end date		●

● is used to indicate a study procedure that requires documentation in the individual eCRF.

○ is used to indicate a study procedure that does not require documentation in the individual eCRF.

x is used to indicate a study procedure that does not require documentation in the individual eCRF as the data will be directly transferred from the provider to GSK.

^a End of AECOPD phone calls/ visits should be scheduled at least every 2 weeks, until the AECOPD has resolved.

Only the contact during which the end date of the AECOPD can be determined will be recorded in the eCRF as the end of the AECOPD contact. All intermediate contacts should be recorded on source documentation.

^b Only applicable if the contact is a visit (not for phone calls).

^c Only if clinically indicated to exclude another cause of worsening of symptoms (e.g. pneumonia).

^d Only if, in the opinion of the investigator, it is safe for the subject.

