6.7.2. Biological samples

Table 10 Biological samples

Sample type	Quantity	Unit	Timepoints	Sub-cohort
Blood for safety assessment * (haematology and biochemistry)	~5.5	mL	
 • Screening Visit (pre-Day 0) • Visit 1 (Day 0) • Visit 2 (Day 7) • Visit 3 (Day 30) • Visit 4 (Day 60) • Visit 5 (Day 67) • Visit 6 (Day 90) • Visit 8 (Day 270) • Visit 10 (Day 450) 	All screened subjects All enrolled subjects
Blood for humoral immunogenicity	~25.5	mL	
 • Visit 1 (Day 0) • Visit 3 (Day 30) • Visit 4 (Day 60) • Visit 6 (Day 90) • Visit 8 (Day 270) • Visit 10 (Day 450) 	All enrolled subjects
Blood for CMI	~40	mL	
 • Visit 1 (Day 0) • Visit 6 (Day 90) • Visit 8 (Day 270) • Visit 10 (Day 450) 	Sub-cohort for CMI
Blood for biomarkers	~12.8	mL	
 • Visit 1 (Day 0) • Visit 10 (Day 450) • During each AECOPD from first vaccination to study conclusion 	All enrolled subjects
Blood for haematology parameters	~2.0	mL	
 • During each AECOPD 	All enrolled subjects
Sputum	1	sample	
 • Screening Visit (pre-Day 0) • Visit 6 (Day 90) • Visit 7 (Day 180) • Visit 8 (Day 270) • Visit 9 (Day 360) • Visit 10 (Day 450) • During each AECOPD from first vaccination to study conclusion 	All screened subjects All enrolled subjects

* Additional blood sample(s) for safety assessment may be taken at the discretion of the investigator if deemed necessary.

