11.8. Analysis of safety

The analysis will be performed on the TVC. If the percentage of vaccinated subjects excluded from the ATP cohort for efficacy is at least 10%, a second analysis will be performed on the ATP cohort for efficacy to complement the first analysis.

The percentage of subjects with at least one **local AE** (solicited and unsolicited), with at least one **general AE** (solicited and unsolicited) and with any AE during the 7-day (day 0 – day 6) or the 30-day (day 0 – day 29) follow-up period will be tabulated after each vaccination and overall with exact 95% confidence interval (CI). The same computations will be done for Grade 3 AEs, for related AEs and for Grade 3 related AEs.

The percentage of subjects/doses reporting each individual solicited local (any grade, Grade 3) and general (any grade, Grade 3, related, Grade 3 related) AE during the 7-day (day 0 to day 6) follow-up period will be tabulated for each group as follows:

- Overall, the percentage of subjects with the symptom and its exact 95% CI.
- Overall, the percentage of doses with the symptom and its exact 95% CI.
- Per study vaccine dose, the percentage of subjects with the symptom and its exact 95% CI.

The exact 95% CIs will be calculated assuming independence between doses. For fever, additional analyses will be performed by 0.5°C increments.

The verbatim reports of **unsolicited** symptoms will be reviewed by a physician and the signs and symptoms will be coded according to the MedDRA Dictionary for Adverse Reaction Terminology. Every verbatim term will be matched with the appropriate preferred term (PT). The percentage of subjects with unsolicited symptoms during the 30-day follow-up period after any study vaccine dose with its exact 95% CI will be tabulated by group and by MedDRA PT. Similar tabulation will be done for the percentage of doses, for Grade 3 unsolicited symptoms, for unsolicited symptoms that resulted in a medically attended visit, for Grade 3 and causally related unsolicited symptoms and for unsolicited symptoms causally related to vaccination.

For each group and for each **haematology/ biochemistry parameter**:

- The percentage of subjects having results below or above the local laboratory normal ranges will be tabulated by time point.
- The maximum grading from Screening up to study conclusion will be tabulated. Grades will be based on the FDA Guidance for Industry “Toxicity Grading Scale for

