11.10. Analysis of impact of the investigational vaccine on AECOPD

The analysis will be performed on the ATP cohort for efficacy. If the percentage of vaccinated subjects excluded from the ATP cohort for efficacy is more than 10%, a second analysis based on the TVC will be performed to complement the first analysis.

The following incidence rates will be computed over a period starting 1 month post-Dose 2 and lasting for 1 year, with 95%CI:

- NTHi-associated moderate and severe AECOPD.
- NTHi-associated all-severity AECOPD.
- All-cause moderate and severe AECOPD.
- All-cause, all-severity AECOPD.

The 95% CI of the incidence rate will be computed using a model which accounts for repeated events. The Generalised linear model assuming the Negative Binomial distribution for the response variable with logarithm as link function, and the logarithm of time for follow-up as an offset variable will be used. If the model does not converge, the Poisson distribution will be used instead of the Negative Binomial one.

Vaccine efficacy (VE) for AECOPD events will be defined as:

$$VE(AECOPD) = 1 - R_{vaccine} / R_{control}$$

with:

- $R_{vaccine}$ = average yearly incidence rate of AECOPD events per subject in the group 10-AS01E.
- $R_{control}$ = average yearly incidence rate of AECOPD events per subject in the Control group.

In case the 95% CI of the VE cannot be estimated, *e.g.* when no event is observed in the group 10-AS01E (leading to a VE of 100%), then an exact procedure will be used to estimate a VE and its 95% CI. This exact procedure will be based on the number of subjects with event instead of on the average number of event per subject in each group.

VE in the prevention of NTHi-associated moderate and severe AECOPD and its 95% CI will be calculated.

VE in the prevention of NTHi-associated all-severity AECOPD, of all-cause moderate and severe AECOPD and of all-cause, all-severity AECOPD and their 95% CI will also be calculated.

The time until first AECOPD as of 1 month post-Dose 2 will be computed with exact 95% CI by group. Subjects who exacerbate before 1 month post-Dose 2 will not be taken into account in this analysis.

The proportion of sputum samples with exact 95% CI obtained at each visit (scheduled visits and AECOPD-driven visits) and positive for bacterial pathogens (overall and by bacterial pathogen) will be computed by group and overall. The exact 95% CI will be estimated assuming independence of bacterial results across sputum samples.

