6.1.7.2. Sputum bacterial/viral results from culture or from PCR

The distribution of the proportion of sputum samples positive given the number of days between start of exacerbation and sample collection will be presented.

The proportion of sputum samples obtained at each - stable and exacerbation - visit and positive for specific bacterial/viral pathogens (overall and by bacterial culture, by bacterial PCR, or by viral species) will be computed. The average infection rate by type of visit will also be calculated.

The bacterial presence in culture versus the bacterial presence in PCR detected in sputum will be tabulated.

The viral infections versus the bacterial presence in PCR detected in sputum will be tabulated.

The incidence of exacerbations and of exacerbations containing Hi, Mcat, Sp, and all bacterial and/or virus that are planned to be tested by the laboratory will be presented.

Statistical Analysis Plan

Study alias & e-track number(s): NTHi-004 (200157)

For specific bacterial pathogens, the quantitative assessment of PCR results will be provided overall, for sputum samples positive in culture, or negative in culture of the specific pathogen.

The same analyses should be performed by taking into account only the sputum that has a good quality.

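### Minor: the exact 95% CI on the overall percentage of doses, and the protocol-only CI on AECOPD-visit sputum positivity, ignore repeat records from the same subject and can under-cover

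*Protocol*

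**What the plan says.** **Doses.** For each solicited symptom, Protocol 11.8 lists three displays per group: the percentage of subjects overall, a pooled dose row ("Overall, the percentage of doses with the symptom and its exact 95% CI"), and the percentage of subjects per dose. It then adds: "The exact 95% CIs will be calculated assuming independence between doses". SAP 6.1.1 (Amendment 1) repeats this. For unsolicited symptoms, after the subject-level percentage with its exact CI, both documents add: "Similar tabulation will be done for the percentage of doses". SAP section 10 gives the exact method as Clopper-Pearson, run in StatXact.

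**Sputum.** Protocol 11.10 asks for the proportion of positive samples at scheduled and AECOPD-driven visits, and says: "The exact 95% CI will be estimated assuming independence of bacterial results across sputum samples". Table 10 in Protocol 6.7.2 schedules sputum "During each AECOPD from first vaccination to study conclusion". Table 8 qualifies this: "Only if, in the opinion of the investigator, it is safe for the subject". Entry requires "at least 1 moderate or severe AECOPD within the 12 months before Screening" (Protocol 5.2), so some subjects can be expected to have more than one sampled episode. SAP 6.1.7.2 specifies "The proportion of sputum samples obtained at each - stable and exacerbation - visit and positive for specific bacterial/viral pathogens" but gives neither a CI nor an independence assumption. SAP Amendment 1 (21 June 2016) is later than Protocol Amendment 3 (15 April 2016), and SAP section 9 does not list the missing CI as a change.

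**The concern.** A Clopper-Pearson interval takes its denominator as a count of independent trials and has no term for clustering. Two doses in one person share that person's tendency to react and to report. Sputum samples from one frequent exacerbator share that person's airway flora. With positive correlation, the interval is narrower than the data support. A reader comparing groups on the pooled dose row, or on AECOPD-visit positivity, would see more precision than there is. Point estimates do not change.

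The displays at risk are few. Subject-level percentages, overall and per dose, use one record per subject. So does sputum at a single scheduled visit. The AECOPD rates come from a negative binomial model that allows for repeated events.

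**Working it through.** **Inputs from the documents.** About 70 subjects per group with 2 doses each (Protocol section 3); two-sided 95% intervals (SAP 7.1.3); Clopper-Pearson (SAP section 10); reported pathogen frequencies at AECOPD of 11-38% for NTHi, 3-25% for *M. catarrhalis* and 4-9% for *S. pneumoniae* (Protocol 1.1.1).

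**Assumed, because neither document gives them.** The within-subject correlation, the symptom incidences, and the number of sampled AECOPDs per subject.

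**Step 1: the nominal level under the plan's own assumption.** With 140 independent records, exact coverage is 95.3-98.6% for incidence 1-80%. The 95% claim holds when correlation is zero, so any shortfall comes from correlation and not from the interval method.

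**Step 2: two correlated doses.** With incidence p at both doses, q = 1 - p and correlation r, one subject has
- P(2 events) = p² + r·p·q
- P(1 event) = 2·p·q·(1 - r)
- P(0 events) = q² + r·p·q

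Convolving over 70 subjects and applying the n = 140 interval gives exact coverage (%):

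| Incidence | r=0 | r=0.1 | r=0.2 | r=0.3 | r=0.5 | r=0.8 |
|---|---|---|---|---|---|---|
| 1% | 98.6 | 98.1 | 97.7 | 97.2 | 96.5 | 95.9 |
| 2% | 97.7 | 97.1 | 96.5 | 95.9 | 94.9 | 93.8 |
| 5% | 97.0 | 96.2 | 95.4 | 94.5 | 92.6 | 90.0 |
| 10% | 96.7 | 95.8 | 94.9 | 93.9 | 91.9 | 88.8 |
| 30% | 95.7 | 94.7 | 93.6 | 92.4 | 90.2 | 86.9 |
| 50% | 96.6 | 95.6 | 94.7 | 93.6 | 91.6 | 88.5 |

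The mechanism is the design effect, 1 + r for two equal-incidence doses. At r = 0.5 the interval should be about √1.5 = 1.22 times as wide.

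**Step 3: unequal incidence at the two doses.** The variance of a subject's total is p₁q₁ + p₂q₂ + 2r√(p₁q₁p₂q₂), while the plan uses 2·p̄·q̄. At r = 0.3 and mean incidence 30%, the plan's value is 2 × 0.3 × 0.7 = 0.42.
- 30%/30%: ratio 1.30, coverage 92.4%.
- 20%/40%: (0.16 + 0.24 + 0.118)/0.42 = 1.23, coverage 93.2%.
- 10%/50%: (0.09 + 0.25 + 0.09)/0.42 = 1.02, coverage 95.5%.

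At r = 0.5, 20%/40% still gives only 91.1%. A difference between doses shrinks the shortfall and can remove it.

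**Step 4: AECOPD-visit sputum.** This was simulated with 70 subjects, gamma-Poisson sample counts (dispersion as the negative binomial parameter), beta-binomial positivity of 5-40%, ICC 0.2-0.6 and 20,000 runs per setting:

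| Sampled AECOPDs per subject | Share of samples from subjects with 2 or more | Coverage |
|---|---|---|
| mean 0.8, dispersion 0.5 | 64% | about 89-97% |
| mean 1, dispersion 1 | 75% | about 84-95% |
| mean 2, dispersion 1 | 89% | about 74-90% |

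With less variable (Poisson) counts at mean 1 and positivity 20-30%, coverage is about 95-96% at ICC 0.1, 93-94% at 0.3 and 91% at 0.5.

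**Step 5: a clustered interval.** This applies Clopper-Pearson to N/deff, with deff estimated from the between-subject variance and floored at 1.
- Doses, with the ordinary exact CI kept when events or non-events are fewer than 3: 94.8-99.0% coverage over 30 scenarios, width ratio 1.01-1.38.
- Sputum: 94.6-96.1% at 25-40% positivity. At mean 2 and ICC 0.2/0.4/0.6 it gives 94.9/93.7/92.5% at 10% positivity and 94.4/91.8/87.7% at 5%. The width ratio is 1.09-1.81.
- First AECOPD sample per subject with an ordinary exact CI: 96.4-98.8%, width ratio 1.27-1.88, with about 34-47 subjects contributing.

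**The case against.** The plan discloses the assumption. Protocol 11.13 calls group comparisons descriptive and advises caution. The solicited-event primary endpoints are defined after each vaccination in all subjects, which the unaffected subject-level rows report; the pooled dose row is supplementary. The percentage-based holding rules in Protocol Table 24 count subjects. All of this stands, and it is why the point is minor. Disclosure does not restore coverage, however.

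The dose shortfall also rests on assumed correlations. Up to 0.2, exact coverage is at least 93.6% at the incidences tabulated, and unsolicited events split by preferred term will often be rare enough to be unaffected. That stands too. The direction under positive correlation and similar incidence at the two doses does not depend on the value chosen.

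For sputum, the later SAP states no CI, and pathogen-related AECOPD incidence is already modelled with allowance for repeats (SAP 6.1.3). This also stands. The first task there is to reconcile the documents, and the flaw matters only if the protocol's CI is kept.

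A reader might infer that sputum coverage is expected to fall to about 74%. The documents do not support that: the figure needs a mean of 2 sampled AECOPDs, strong overdispersion and ICC 0.6 together, and none of these is given.

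**Conclusion.** The point holds as a minor one. The dose-level exact CI treats paired records as independent and under-covers when correlation is moderate and the symptom is not rare: about 95/93/90% at 5% incidence and 94/90/87% at 30%, for correlation 0.2/0.5/0.8. These figures assume 70 subjects with both doses recorded and equal incidence at each dose. At correlation of about 0.1 or less, or at 1% incidence, coverage is near or above 95%.

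The same flaw is in the protocol's CI for AECOPD-visit sputum where subjects give repeat samples. Its size cannot be fixed from the documents, because it depends on AECOPD counts and ICC.

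A reader might infer that the primary safety conclusions or the holding rules are compromised. The documents do not support that: subject-level intervals are planned beside the dose row, and no decision rule uses either interval.

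**What to change.** **Doses (Protocol 11.8, SAP 6.1.1).** Delete the independence assumption for the pooled dose row and do one of the following:
- Use a subject-clustered interval, for example Clopper-Pearson on N/deff with deff at least 1. Keep the ordinary exact CI when events or non-events are fewer than 3, and footnote the switch.
- Print the dose percentage without a CI and rely on the planned subject-level intervals.

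**Sputum at AECOPD-driven visits.** First reconcile Protocol 11.10 with SAP 6.1.7.2 on whether this proportion carries a CI. If it does, cluster by subject over all AECOPD samples. Footnote that the interval may still under-cover at positivity of about 10% or less when some subjects exacerbate often (about 92-95% at 10% positivity, about 88-94% at 5%). A first-sample-per-subject exact CI may be added, labelled as describing the first episode only. It should not replace the all-episode display, because the tertiary endpoint covers every AECOPD (Protocol 11.3).

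**Cost.** SAP wording and a short program, with no new data. Clustered intervals are about 1.0-1.4 times as wide for doses and 1.1-1.8 times for sputum, and they are no longer strictly exact. The sparse-count rule can change the method between adjacent table rows. The optional first-sample interval is 1.3-1.9 times as wide and discards repeat samples. Dropping the dose CI costs only that interval.

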^e Only for AECOPD visits from first vaccination up to 6 months post-Dose 2 (Day 240).

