9.3. Detecting and recording adverse events, serious adverse events and pregnancies

9.3.1. Time period for detecting and recording adverse events, serious adverse events and pregnancies

All AEs starting within 29 days following administration of each dose of study vaccine must be recorded into appropriate section of the eCRF, irrespective of intensity or whether or not they are considered vaccination-related.

All AEs/ SAEs leading to withdrawal from the study will be collected and recorded from the time of the first receipt of study vaccine until study conclusion.

The time period for collecting and recording pIMDs will begin at the first receipt of study vaccine and will end at study conclusion. See section [9.4](#) for instructions on reporting of pIMDs.

The time period for collecting and recording SAEs will begin at the first receipt of study vaccine and will end at study conclusion. See Section [9.4](#) for instructions on reporting of SAEs.

In addition to the above-mentioned reporting requirements for SAEs and in order to fulfil international reporting obligations, SAEs that are related to study participation (*i.e.* protocol-mandated procedures, invasive tests, a change from existing therapy) or are related to a concurrent GSK medication/vaccine will be collected and recorded from the time the subject consents to participate in the study until she/ he is discharged from the study. See Section [9.4](#) for instructions on reporting of SAEs.

The time period for collecting and recording pregnancies will begin at the first receipt of study vaccine and will end 6 months following administration of the last dose of study vaccine. See section [9.4](#) for instructions on reporting of pregnancies.

The time period for collecting and recording intercurrent medical conditions that require medical attention will begin at the first receipt of study vaccine and will end at study conclusion.

An overview of the protocol-required reporting periods for AEs, SAEs, and pregnancies is given in [Table 21](#).

Table 21 Reporting periods for adverse events, serious adverse events and pregnancies

Visit	Screening Visit*	V1	6 days	29 days	V4	6 days	29 days	6 months	Study Conclusion
Timepoint		Dose 1	post-Dose 1	post-Dose 1	Dose 2	post-Dose 2	post-Dose 2	post-Dose 2	D240 D450
Solicited local and general AEs									
Unsolicited AEs									
AEs/ SAEs leading to study withdrawal									
plMDs									
SAEs									

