11. STATISTICAL METHODS

11.1. Primary endpoints

- Occurrence of each solicited local adverse event (AE), during the 7-day follow-up period (*i.e.* day 0 - 6) following each vaccination, in all subjects.
- Occurrence of each solicited general AE, during the 7-day follow-up period (*i.e.* day 0 - 6) following each vaccination, in all subjects.
- Occurrence of any unsolicited AE, during the 30-day follow-up period (*i.e.* day 0 - 29) following each vaccination, in all subjects.

- Occurrence of each haematological/ biochemical laboratory abnormality at Day 0, Day 7, Day 30, Day 60, Day 67, Day 90, Day 270 and Day 450, in all subjects.
- Occurrence of any potential immune-mediated disease (pIMD) from first vaccination up to study conclusion, in all subjects.
- Occurrence of any serious adverse event (SAE) from first vaccination up to study conclusion, in all subjects.

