Healthy Adults and Adolescent Volunteers Enrolled in Preventive Vaccine Clinical Trials" (see **APPENDIX C**).

The number of subjects who experienced any **pIMD** or any **SAE** from first vaccination up to 6 months post-Dose 2 will be reported.

The number of subjects who experienced any **AE leading to study withdrawal**, from first vaccination up to study conclusion, or any **SAE related to study participation of concurrent GSK medication/ vaccination**, during the entire study period, will be reported.

Pregnancy exposures from first vaccination up to 6 months after last vaccination and pregnancy outcomes will be described in detail.

The percentage of subjects/ dose using **concomitant medication/ product** (any medication/ product, any antipyretic and any antipyretic taken prophylactically, respectively) during the 7-day follow-up period (day 0 – day 6) and during the 30-day follow-up period (day 0 – day 29) will be summarised per group for each dose and overall per dose.

11.8.1. iSRC safety evaluations

Unblinded review of safety data will be done during iSRC evaluations (refer to Section **9.10** for more information). No individual clinical study report will be written as a result of these safety evaluations.

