4. ENDPOINTS

4.1. Primary endpoints

- Occurrence of each solicited local adverse event (AE), during the 7-day follow-up period (*i.e.* day 0 - 6) following each vaccination, in all subjects.
- Occurrence of each solicited general AE, during the 7-day follow-up period (*i.e.* day 0 - 6) following each vaccination, in all subjects.
- Occurrence of any unsolicited AE, during the 30-day follow-up period (*i.e.* day 0 - 29) following each vaccination, in all subjects.
- Occurrence of each haematological/ biochemical laboratory abnormality at Day 0, Day 7, Day 30, Day 60, Day 67, Day 90, Day 270 and Day 450, in all subjects.
- Occurrence of any potential immune-mediated disease (pIMD) from first vaccination up to study conclusion, in all subjects.

Statistical Analysis Plan

Study alias & e-track number(s): NTHi-004 (200157)

- Occurrence of any serious adverse event (SAE) from first vaccination up to study conclusion, in all subjects.

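### The SAE and pIMD counts in Protocol 11.8 and SAP 6.1.1 stop six months after Dose 2, but the primary endpoints they serve run to study conclusion

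*Protocol*

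**What the plan says.** Protocol 11.8 sets the window for both events in one sentence: the number of subjects with any pIMD or any SAE "from first vaccination up to 6 months post-Dose 2 will be reported". SAP Amendment 1, Section 6.1.1, repeats it. The day number for that point is in Protocol 6.5.2, Table 8, footnote e, which limits pregnancy reporting at AECOPD visits to the period "from first vaccination up to 6 months post-Dose 2 (Day 240"). Table 21 in Protocol 9.3.1 gives the same day and puts study conclusion at Day 450.

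The endpoint definitions run longer. Protocol 11.1 lists "Occurrence of any serious adverse event (SAE) from first vaccination up to study conclusion, in all subjects", and SAP 4.1 lists "Occurrence of any potential immune-mediated disease (pIMD) from first vaccination up to study conclusion, in all subjects". Each document defines both endpoints in this way.

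Collection follows the endpoint. Protocol 9.3.1 states for SAEs: "The time period for collecting and recording SAEs will begin at the first receipt of study vaccine and will end at study conclusion". For pIMDs it states: "The time period for collecting and recording pIMDs will begin at the first receipt of study vaccine and will end at study conclusion".

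Protocol 11.14.1 and SAP 8.1 both include SAEs and pIMDs to Day 450 in the final analysis.

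**The concern.** The two safety-methods sentences are the only places in the supplied documents that define the SAE/pIMD summary as a count of subjects. The sequence-of-analyses sections give a scope and define no statistic. A programmer working from the methods section would cut at Day 240, and one working from SAP 8.1 would go to Day 450. Under the first reading, the table presented for two primary endpoints would not measure those endpoints as defined.

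Safety is the primary objective, and vaccine-induced autoimmune disease is the only risk in the risk table (Protocol 1.3.1), so late pIMDs matter. Late SAEs are also foreseeable. Entry requires at least one moderate or severe AECOPD in the preceding 12 months (Protocol 5.2), severe AECOPD means hospitalisation (Table 2), and AECOPD that meet the SAE definition are reported as SAEs (9.2.1).

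**Working it through.** **1. Compare end dates.**

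| Item | Endpoint or collection ends | Count in Protocol 11.8 ends |
|---|---|---|
| Laboratory grading | Day 450 (11.1) | Study conclusion |
| AEs leading to withdrawal | Study conclusion (9.3.1) | Study conclusion |
| Pregnancies | 6 months after last dose (9.3.1) | 6 months after last dose |
| SAEs and pIMDs | Study conclusion (11.1, 9.3.1) | 6 months after Dose 2 |

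The relevant 11.8 wording is "The maximum grading from Screening up to study conclusion will be tabulated" for laboratory grading and "Pregnancy exposures from first vaccination up to 6 months after last vaccination" for pregnancies. Of these four windows, only the SAE/pIMD one ends before its endpoint or collection period does.

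**2. Could it be an intended separate cut?** SAP 8.1 names two analyses, one to Visit 6 (Day 90) and one to Day 450. Six months after Dose 2 matches neither, and no text calls the count additional. In the superseded SAP version 1, the Day 90 section (6.1.2) counted to 30 days after Dose 2, and the six-month wording stood in the final-analysis section (6.2.2). It was therefore not an interim window.

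**3. Size of the gap (nominal days).**
- Dose 2 is at Day 60, so six months later is 60 + 180 = Day 240, as the protocol states.
- Gap: 450 − 240 = 210 days, and 210/450 = 46.7%.
- Scheduled visits with SAE reporting inside the gap: Visits 8, 9 and 10 (Days 270, 360 and 450).
- Person-time at the target of 140 subjects with no dropout: 140 × 210/365.25 = 80.5 of 140 × 450/365.25 = 172.5 person-years. The vaccine group contributes 70 × 210/365.25 = 40.2.

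**4. Illustration on the protocol's own sample-size scale.** Protocol 11.4 claims, with 70 subjects per group, a better than 50% chance of seeing an event of 1% incidence and better than 97% at 5%. These figures reproduce:
- 1 − 0.99^70 = 50.5%
- 1 − 0.95^70 = 97.2%

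Section 11.4 attaches no time window. Assume that 1% and 5% are cumulative risks to Day 450, with constant hazard and full follow-up. To Day 240 the exponent becomes 70 × 240/450 = 37.33:
- 1 − 0.99^37.33 = 31.3%
- 1 − 0.95^37.33 = 85.3%

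Event timing is unknown. If a share f of subjects with an event have their first one by Day 240, the chance of counting at least one subject is 1 − (1 − p·f)^70:

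| f | p = 1% | p = 5% |
|---|---|---|
| 0.25 | 16.1% | 58.5% |
| 0.50 | 29.6% | 83.0% |
| 0.75 | 41.0% | 93.1% |
| 1.00 | 50.5% | 97.2% |

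**The case against.** The strongest reply is that the plan already covers the later period. Protocol 11.14.1 and SAP 8.1 commit the final analysis to Day 450, both endpoint lists run to study conclusion, and neither methods sentence says that its count is exclusive. Someone reading the whole SAP would probably work to Day 450. This point stands as a limit on the harm: the plan contradicts itself on the window and does not abandon the later events. It does not remove the conflict, because the sentence that defines the statistic is the one with the short window.

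Several smaller points also stand:
- All analyses are descriptive, and no inference or sample size depends on this count.
- Individual listings and 24-hour reporting of SAEs and pIMDs do not depend on this table.
- The separate tables, figures and listings annex named in the SAP was not available and may fix the window. It would not correct the two sentences.
- The detection probabilities rest on assumptions that the documents do not make, and they apply only if the short window is followed.
- The comparison with neighbouring windows concerns end dates. Laboratory grading starts at Screening while its endpoint starts at Day 0, so its start does not match exactly.

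**Conclusion.** The concern holds. As written, Protocol 11.8 and SAP 6.1.1 specify a count for two primary safety endpoints that stops 210 nominal days (47%) before the endpoints do, and any subject whose first SAE or pIMD falls in that period is left out. This is a wrong window in the specification and involves no loss of data.

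It should be fixed, but it does not threaten the trial. Confidence in the textual conflict is high. Whether the produced tables would be wrong depends on which sentence the programmer follows and on the unseen annex. The 47% depends only on the nominal visit days. The person-years also assume full enrolment and no dropout. The fall from 50.5% to 31.3% (or from 97.2% to 85.3%) is an illustration under constant hazard, and the rating does not depend on it.

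**What to change.** In Protocol 11.8 and SAP 6.1.1, end the window for pIMDs and SAEs at study conclusion instead of six months after Dose 2. If a six-month count is also wanted, show it as an additional row, labelled as such and not as the primary endpoint. Protocol 11.14.1 and SAP 8.1 need no change. Check that the tables annex uses the same window.

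The cost is one phrase in one sentence of each document, plus one date cut-off if the table program already uses six months. No new data are needed. Protocol amendments go through ethics review (Protocol 6.1), so the protocol wording could go into the next amendment. If none is planned, correct the SAP, record the change in its Section 9, and explain it in the final study report as Protocol 11.14 requires.
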